## Section 13 – 30-day Overall mortality (Yes/No)

## Section 14 – Post-cholecystectomy 30-day morbidity and mortality

- ! Post-cholecystectomy morbidity (Yes/No)
- ! Post-cholecystectomy mortality (Yes/No)
- ! 30-day hospital readmission (No/Yes-due to surgical complications/Yes-due to recurrent pancreatitis while awaiting interval cholecystectomy)

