#### **Primary outcomes**

- ! 30-day mortality: assessed by the number of AP patients with biliary etiology deceased during the non-pandemic period (2019) and the Covid-19 pandemic period (2020)
- ! 30-day morbidity: assessed by the number of AP patients with biliary etiology who experienced any type of AP-related complication within 30-days from the hospital admission during the non-pandemic period (2019) and the Covid-19 pandemic period (2020)

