#### **Study population**

All consecutive adult patients admitted to the participating surgical departments with a clinical and radiological diagnosis of biliary AP (with and without concomitant cholecystitis) between 01/01/2019 and 31/12/2020. Patient data will be retrospectively analyzed and demographic characteristics, comorbidity status, clinical and radiological findings, treatment strategies, 30-day morbidity and mortality will be evaluated.

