#### **Informed consent**

Due to its retrospective design, this observational study will not attempt to change or modify the laboratory or clinical practices of the participating physicians. Consequently, informed consent will not be required.

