## Section 2 – Demographic Characteristics

- ! Year of hospital admission for acute biliary pancreatitis (2019 Vs. 2020)
- ! Patient age
- ! Sex (Female Vs. Male)
- ! Covid-19 status on admission (Negative/Positive/Untested)

- ! Previous episodes of biliary pancreatitis (Yes/No)
- ! Admitting speciality (HPB surgery/General Surgery/Internal Medicine/Gastroenterology)

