## Section 10 – 30-day Morbidity

- ! Gastric outlet obstruction (Yes/No)
- ! Pseudocyst (Yes/No)
- ! Infected necrosis (Yes/No)
- ! Endoscopic drainage of pseudocyst/walled-off necrosis (Yes/No)
- ! CT-guided fine needle aspiration in case of infected pseudocyst/walled-off necrosis (Yes/No)
- ! Surgical necrosectomy (Yes-laparoscopic/Yes-open/No)
- ! Timing of surgical necrosectomy (< 2 weeks from the onset of symptoms/2-4 weeks)>4 weeks)
- ! Setting of surgical necrosectomy (Upfront/After failure of endoscopic necrosectomy/After failure of endoscopic and percutaneous necrosectomy)
- ! Cystogastrostomy (Yes-endoscopic/Yes-surgical/No)
- ! Abdominal compartment syndrome (Yes/No)
- ! Open abdomen (Yes/No)
- ! Timing of re-exploration (24-48 hours/48-72 hours/>72 hours)
- ! Bleeding (Yes/No)
- ! Bowel ischemia (Yes/No)

- ! Bowel fistula (Yes/No)
- ! Necrotizing cholecystitis (Yes/No)

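### The 30-day outcome fields have no code for unknown status and the CRF records no discharge or last-contact time, so a patient unseen after discharge can be entered as event-free without trace

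*Combined protocol and SAP*

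**What the plan says.** Both primary outcomes run to day 30. Under Primary outcomes, morbidity counts patients "who experienced any type of AP-related complication within 30-days from the hospital admission". The mortality definition beside it gives no time origin. The Study population section says only that "treatment strategies, 30-day morbidity and mortality will be evaluated", from data analysed retrospectively.

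The CRF records these outcomes as follows:

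- Section 13: "30-day Overall mortality (Yes/No", with no third option.
- Section 10: the complication items are binary, for example "Infected necrosis (Yes/No". Some procedure items carry route, timing or setting categories, but none has an unknown option.
- Section 14: "30-day hospital readmission (No/Yes-due to surgical complications/Yes-due to recurrent pancreatitis while awaiting interval cholecystectomy", again with no unknown option. The secondary outcome counts readmission from discharge, not from admission.
- Section 2: the admission is placed in time only by "Year of hospital admission for acute biliary pancreatitis (2019 Vs. 2020".

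CRF Sections 1 to 14 list no discharge date or status, length of stay, date of death or last contact. A not-known category does appear elsewhere, in "Covid-19 status on admission (Negative/Positive/Untested". The sections on data collection, data management and statistical analysis do not describe how events after discharge are found, any check of follow-up completeness, or any rule for missing outcomes.

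**The concern.** A 30-day outcome in a retrospective chart study is complete only if each patient's status at day 30 is known. The Background says the course is rapidly favourable in about 80% of cases, so many patients probably leave hospital well before day 30. After that, the treating hospital's record may contain nothing. A No in Section 13 can mean that the patient was known to be alive at day 30, or only that no death was noted before the chart ended. The dataset cannot separate the two.

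Two things are at stake. Absolute 30-day rates may be too low. The comparison of 2019 with 2020 may also be distorted if events after discharge were captured less well, or better, in one year. The Background section on Covid-19 describes postponed endoscopy and more conservative treatment in 2020, so a change in return visits is plausible, but the plan gives no figure for it. The primary objective, which relates disregarded guideline items to outcome, is exposed in the same way if capture varies with the item. Because the information is not collected, the analysis cannot detect or bound the problem afterwards.

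**Working it through.** **Inputs from the documents.** Mortality of about 10% and at least 200 patients per year (Sample size); P < 0.05 (Statistical analysis). No loss or capture rate is given, so every capture figure below is an assumption.

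**The plan's own figure.** The 200 per group cannot be reproduced because no alternative mortality rate is stated. Solving backwards at one-sided 0.05 and 80% power from 10%, it corresponds to a rise to 18.7%. The point does not depend on this, but the value serves as a yardstick.

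**1. Effect on the recorded rate.** If a share u of deaths is missed and entered as No, recorded rate = true rate × (1 − u). From a true 10%:

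- u = 5%: 9.5%
- u = 10%: 9.0%
- u = 20%: 8.0%

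**2. Equal capture in both years.** With no true difference, the bias between years is nil. With a true difference, it shrinks. Against 10% versus 18.7%, power at 200 per group falls from 80% to 77.9%, 75.6% and 70.6% for u = 5%, 10% and 20%.

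**3. Unequal capture, true mortality 10% in both years.**

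- Scenario A: 15% of deaths occur after discharge, captured in 80% of cases in 2019 and 40% in 2020. 2019: 10% × (1 − 0.15 × 0.20) = 9.7%. 2020: 10% × (1 − 0.15 × 0.60) = 9.1%. False fall: 0.6 points.
- Scenario B: 5% of all deaths missed in 2019 and 20% in 2020. 10% × 0.95 = 9.5%; 10% × 0.80 = 8.0%. False fall: 1.5 points (odds ratio 0.83).

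Reversing the years reverses the sign. For scale, the standard error of the difference at 200 per group is √(2 × 0.10 × 0.90 / 200) = 3.0 points. In scenario B the two-sided test at 0.05 rejects in 8.3% of studies at 200 per group and 22.1% at 1000 per group, so the problem grows with study size.

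**4. Morbidity.** Assume a true rate of 20% in both years, 30% of complications first appearing after discharge, and the capture of scenario A. 2019: 20% × (1 − 0.30 × 0.20) = 18.8%. 2020: 20% × (1 − 0.30 × 0.60) = 16.4%. False fall: 2.4 points.

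**5. Why restricting to known status is not the answer.** Take 1000 patients per year, 100 true deaths, and scenario A for deaths. Suppose that day-30 survival is also confirmed for 80% of the 900 survivors in 2019 and 40% in 2020.

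- 2019: 97 / (97 + 720) = 11.9%
- 2020: 91 / (91 + 360) = 20.2%

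A true null becomes a false rise of 8.3 points, far larger than the 0.6-point fall it was meant to remove and close to the 8.7 points (10% to 18.7%) of the yardstick above.

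**6. What an unknown code allows.** In the same example the unknowns number 1000 − 97 − 720 = 183 in 2019 and 1000 − 91 − 360 = 549 in 2020. Counting them all as alive, then all as dead, gives 9.7% to 28.0% and 9.1% to 64.0%. Both intervals contain the true 10%. With lighter loss they are narrower: 10% unknown and 10% mortality among the rest gives 9% to 19%.

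**The case against.** The strongest reply is that the CRF section is a list of variables, not a database specification. Nothing in it makes a field mandatory or forbids a blank, and nothing rules out a telephone call, a registry check or clinic records. That stands. A reader might infer that every unseen patient is entered as an event-free survivor, or that patients are never contacted. The documents say neither. The Informed consent section says "Due to its retrospective design, this observational study will not attempt to change or modify the laboratory or clinical practices", which concerns practice and consent, not how outcomes are found. But if blanks, calls and registry checks are left to each centre, completeness varies between centres and goes unrecorded, which is the same defect.

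A reader might also infer that missed events fall mainly in patients discharged early without definitive treatment, so that harm from disregarded guideline items is hidden. The documents do not support that direction. On the Sample size section's figures, patients with organ failure contribute 20% × 30% = 6 of the 10 points of mortality, and they seem the least likely to leave early. Several audited items, such as antibiotic prophylaxis or CT timing, have no evident link to visibility after discharge.

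The CRF also gives partial cover: readmission and post-cholecystectomy outcomes (Section 14), repeat CT at 15 to 30 days or later (Section 7), and necrosectomy after 4 weeks (Section 10). A positive entry in one of these can show that a patient was seen late. A negative entry does not show that the patient was seen at all.

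Finally, the mortality biases shown are well below the 3-point standard error at 200 per group. That is fair at the planned minimum, and it limits the weight of the point.

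**Conclusion.** The point holds in a limited form. For both primary outcomes and for readmission, the data cannot distinguish a patient confirmed event-free from one last seen at discharge. An unseen patient can be entered as event-free, and nothing collected would show it. Where that happens, recorded rates are too low.

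Whether the comparison between years is biased, and in which direction, depends on capture after discharge, which the documents do not quantify. Under equal capture the bias between years is nil when true rates are equal. Under the assumed unequal capture it is -0.6 to -1.5 points for mortality, from a true 10% in both years, and -2.4 points for morbidity in the single scenario tried. These figures illustrate scale; they are not estimates. The change is worth making because it is cheap before data entry and because no later analysis can recover what was not recorded.

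**What to change.** **CRF**

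- Recode Section 13 as: died in hospital; died after discharge by day 30; known alive at day 30; discharged alive, day-30 status unknown.
- Add an unknown option to the readmission field and to the Section 10 complications that can arise after discharge. Known vital status does not establish freedom from complications.
- Add days from admission to discharge and days from admission to last contact. As intervals, they keep no dates, consistent with the plan's exclusion of identifiable data.

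**Protocol and analysis**

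- State the index admission as day 0 for both primary outcomes, and state how status after discharge is to be found.
- Report in-hospital death and in-hospital complications for all patients alongside the 30-day outcomes.
- Report completeness of day-30 status by year and by key guideline item.
- Show 30-day results with best-case and worst-case bounds for unknown status. Do not make the analysis restricted to known status the main one: in-hospital deaths always have known status, while discharged survivors often do not.

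**Cost.** One recoded field, an added option and two interval fields per patient, read from the same chart. Data entry is planned from March 2021, when every patient admitted by the end of 2020 is past day 30, so no extra follow-up time is needed. The price is that some 30-day outcomes will appear as unknown, with wider bounds.

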#### Background

Acute pancreatitis (AP) is an inflammatory disease of the pancreas, most commonly caused by gallstones or excessive alcohol use. It represents a management challenge and a significant healthcare burden. The incidence of AP ranges globally from 5 to 30 cases per 100.000 inhabitants/year, and there is evidence that the incidence has been rising in recent years. The overall case-fatality rate for AP is roughly 5%, and it is expectedly higher for more severe stages of the disease [1, 2]. In most cases (80%), the outcome of AP is rapidly favorable [3]. However, acute necrotizing pancreatitis (ANP) may develop in up to 20% of cases and is associated with significant rates of early organ failure (38%), needing some surgical/endoscopic intervention (38%), and death (15%) [4].

In the United States, AP is a leading cause of inpatient care among gastrointestinal conditions: more than 270.000 patients are hospitalized for AP annually, at an aggregate cost of over 2.5 billion dollars per year [5]. In Europe, the UK incidence of AP is estimated as 15-42 cases per 100.000/year and is rising by 2.7% each year [6].

Several scientific societies published their clinical practice guidelines making recommendations on the management of AP [7] (Table\_1-4). These guidelines' main topics are the diagnosis, antibiotic treatment, management in the intensive care unit, surgical and operative management, and open abdomen management.

Audits about biliary AP have been performed in Italy, Germany, France, and England, with quite disappointing results [8-11]. Indeed, in these audits, the treatment of biliary AP differed substantially from the recommendations. For example, less than 15% of the responders stated that they strictly followed all recommendations included in the guidelines in Germany, and 25.8% of patients did not receive definitive treatment for biliary AP within one year in the UK [12].

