#### Secondary outcomes

- ! Early definitive treatment rate in 2019 vs. 2020: defined as treatment in accordance with the current guidelines (cholecystectomy or ERCP with endoscopic sphincterotomy during the same hospital admission or within 2 weeks of discharge)
- ! 30-day hospital readmission rate in 2019 vs. 2020: defined as hospital readmission within 30days from discharge for recurrent biliary AP while awaiting interval cholecystectomy, or due to post-cholecystectomy complications
- ! Predictive factors of morbidity and mortality in patients with biliary AP

The compliance of surgeons to the most up-to-date international guidelines on biliary AP will be assessed through the analysis of the following attitudes:

! Use of scoring systems for the diagnosis and severity grading of biliary AP

- ! Use of lipase dosage (for the diagnosis) and CRP (for the severity grading) during the diagnostic workup
- ! Use of Ultrasound scan, CT scan, MRCP, and endoscopic Ultrasound scan (EUS) in the correct way and timing
- ! Use of early ERCP and sphincterotomy in case of cholangitis and/or choledocholithiasis
- ! Use of percutaneous and/or endoscopic drainage in case of infected pseudocyst or necrosis
- ! Timing of surgical necrosectomy
- ! Timing of re-laparotomy in case of open abdomen strategies
- ! Use of prophylactic antibiotics/antifungals
- ! Use of somatostatin analogs
- ! Use of early enteral feeding
- ! Use of early definitive treatment strategies, including cholecystectomy and/or ERCP and sphincterotomy

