#### Sample size

Studies on biliary AP found a mortality rate of approximately 10%. Patients with biliary AP tend to have a higher mortality than patients with alcoholic pancreatitis. However, this rate has been falling over the last 2 decades as improvements in supportive care have been initiated. In patients with severe disease (organ failure), who account for about 20% of presentations, mortality is approximately 30%. This rate has not decreased in the past 10 years.

We estimate that a minimum of 200 patients per group (2019 vs. 2020) would yield a power of 0.80 (1β) to establish whether changes in clinical care for patients with biliary AP during the Covid-19 pandemic has impacted on overall mortality using a one-sided significance a level of 0.05 (5%) with power sample size calculator (sealedenvelope.com).

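### The 30-day readmission item has no code for patients who died before discharge and the outcome has no stated denominator, so in-hospital deaths may be counted as not readmitted

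*Combined protocol and SAP*

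**What the plan says.** In the protocol's Secondary outcomes section, 30-day readmission is compared between 2019 and 2020 and is "defined as hospital readmission within 30days from discharge for recurrent biliary AP while awaiting interval cholecystectomy", or for complications after cholecystectomy. The section does not say which patients form the denominator.

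CRF Section 14, headed as post-cholecystectomy morbidity and mortality, collects the outcome as "30-day hospital readmission (No/Yes-due to surgical complications/Yes-due to recurrent pancreatitis while awaiting interval cholecystectomy". These are the only three answers; none covers death before discharge, not applicable or unknown.

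Death is recorded in two places. CRF Section 13 has "30-day Overall mortality (Yes/No", and Section 14 has "Post-cholecystectomy mortality (Yes/No". Neither has a date or says whether death came before or after discharge. CRF Sections 1 to 14 contain no discharge date, discharge status or length of stay, and the only timing of admission is the calendar year.

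The Statistical analysis section assigns categorical data to chi-squared or Fisher's exact tests and has no rule for patients who died.

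**The concern.** A patient who dies during the index stay never becomes at risk of readmission. The natural denominator is patients discharged alive, but the plan neither states it nor collects what is needed to build it.

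Of the three listed answers, No is the only one that is literally true for an in-hospital death. If sites use it and the analyst divides by all patients, the year with more in-hospital deaths shows a lower readmission rate for that reason alone. If some sites enter No and others leave a blank, the denominator varies by site, and a blank cannot be told apart from missing data.

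The Aim of the study section asks whether pandemic care led to more adverse outcomes. If mortality was indeed higher in 2020, the error would make 2020 readmission look lower than it was.

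**Working it through.** **The plan's own figure.** The documents give no readmission rate and no sample size for this outcome, so there is nothing to reproduce. The minimum of 200 patients per group concerns mortality.

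**Inputs**
- From the documents: mortality of about 10% in biliary AP (Sample size) and case fatality of about 5% in all AP (Background). Neither is described as in-hospital mortality; using them as such is an assumption.
- Assumed: a comparator mortality of 15%; readmission r among patients discharged alive of 5% to 25%, equal in the two years.

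**Step 1: effect of the coding.** Suppose a share m of patients die before discharge, are entered as No and stay in the denominator. Then

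recorded rate = r × (1 − m)

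With equal r, the ratio of recorded rates is

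(1 − m₂₀₂₀) / (1 − m₂₀₁₉)

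| m 2019 | m 2020 | Ratio |
|---|---|---|
| 10% | 10% | 0.90/0.90 = 1.000 |
| 5% | 10% | 0.90/0.95 = 0.947 |
| 10% | 15% | 0.85/0.90 = 0.944 |

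**Step 2: absolute size.** At r = 15% and mortality of 10% vs 15%, the recorded rates are 0.15 × 0.90 = 13.5% and 0.15 × 0.85 = 12.75%, a false difference of −0.75 points. Over r from 5% to 25%, it runs from −0.25 to −1.25 points.

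**Step 3: effect on the test.** In the same scenario (r = 15%, 10% vs 15%) with 200 per group, the chance of a two-sided significant result in the biased direction is about 4%, against 2.5% without bias. At an assumed 2000 per group it is about 10%.

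**Step 4: can the 30-day mortality item repair it?** Let f be the share of in-hospital deaths that occur by day 30, and assume that deaths between discharge and day 30 are negligible. After all 30-day deaths are excluded,

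recorded rate = r × (1 − m) / (1 − f·m)

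For 10% vs 15%:
- f = 80%: (0.85/0.88) / (0.90/0.92) = 0.966/0.978 = 0.987
- f = 90%: (0.85/0.865) / (0.90/0.91) = 0.983/0.989 = 0.994

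The values of f are assumptions. On them, the bias falls from about 5.5% to about 1%. The repair is inexact for two reasons:
- It misses in-hospital deaths after day 30. These are plausible: the section on pancreatic necrosis describes a prolonged course and late mortality, and CRF Section 10 has a category for necrosectomy after four weeks.
- It drops patients who died after discharge but within 30 days. They were at risk, and any who had been readmitted were true events.

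The starting point of the mortality window is also unclear. The Primary outcomes section counts morbidity from admission but names no start for mortality, while readmission runs from discharge. The post-cholecystectomy death item does not help, since it covers only operated patients and also lacks date and place.

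**The case against.** The best counter-argument is that nothing in the documents tells sites to enter No for a patient who died. A clock that starts at discharge already implies a discharged patient. Other conditional CRF items (timing and setting of necrosectomy, timing of re-exploration) also lack a not-applicable code and must be left blank when they do not apply. Because Section 14 is headed as post-cholecystectomy, the item may not be completed at all for patients who died without surgery. This stands: a reader might infer that in-hospital deaths do count as No, but the documents show only that they may. Unlike those conditional items, however, this one does offer No.

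Second, an analyst can exclude 30-day deaths with an item that directly precedes Section 14. This also stands, with the limits in step 4, but the plan does not specify the exclusion.

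Third, 30-day mortality is a primary outcome compared over the same two years, so a mortality difference would be reported beside the readmission result. That limits the risk of misreading but does not give readmission a denominator.

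A reader might also infer a larger bias. At a 10% baseline, 200 per group with 80% power and one-sided 5% corresponds to a 2020 rate of about 18.7%, and 0.813/0.90 = 0.90. But 18.7% is solved backwards from the sample size. The Sample size section states no comparator rate, and a detectable rise is not an expected one. The 0.90 also assumes no exclusion of deaths; with 30-day deaths excluded it becomes 0.956/0.978 = 0.977 (f = 80%) or 0.978/0.989 = 0.988 (f = 90%).

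**Conclusion.** The gap is real and small. The outcome runs from discharge, the item cannot record that a patient was never discharged, and the data collected do not allow the discharged-alive denominator to be recovered exactly.

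If in-hospital deaths are entered as No and kept in, the 2020/2019 ratio is about 0.945 at 5% vs 10% or 10% vs 15% mortality. If 30-day deaths are excluded, it is about 0.99 at 10% vs 15%. Both results rest on equal readmission among survivors, on the assumed mortality figures being in-hospital, and on the coding described. With equal mortality in the two years, the comparison is unbiased.

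A reader might extend the point to early definitive treatment and conclude that withholding it would look better on readmission. The documents do not support this. Readmission is specified only by year, the regression models address morbidity and mortality, and the Aim of the study section states no expectation about mortality by early treatment.

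This is a cheap improvement.

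**What to change.** - In CRF Section 14, add the code *Not applicable – died before discharge* to the readmission item, or add a discharged-alive Yes/No item to the CRF.
- In Secondary outcomes, define the readmission rate among patients discharged alive.

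The cost is one CRF code or item, one phrase in the protocol and a slightly smaller denominator. Clinical care is unaffected. For records already entered, sites would need to complete the new code from the patient's chart.
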